3.4.2 Leukapheresis

All research participants will be encouraged to periodically undergo a leukapheresis as outlined in the protocol. If the research participant does not agree to the leukapheresis the standard 200 cc of peripheral blood will be obtained. In addition, any research participant demonstrating an interesting immunological response may be asked to undergo leukapheresis to obtain greater numbers of lymphocytes for research purposes. This may include physical responses thought to be related to the vaccine (including, but not limited to vaccine site flares) or interesting laboratory responses (including, but not limited to mesothelin-specific CD8+T cell responses). There will be at least two weeks between additional leukapheresis procedures. As of Amendment #8, research bloods are no longer required to be collected.

Prior to the leukapheresis, subjects will be evaluated by the Hematopoietic and Therapeutic Support (HATS) Center to determine if their vascular access appears to be adequate for the leukapheresis procedure.

If the research participant had a leukapheresis within two weeks (+/- 14 days) of a protocol-specified research sample collection point, the peripheral blood lymphocyte collection of 200 cc of blood and the peripheral blood lymphocyte collection need not be repeated.

3.4.3 Evaluation for Safety and Anticipated Toxicities

Severe toxicities are unlikely, based on information from previous GM-CSF gene vaccine studies completed here at Johns Hopkins Hospital trials, including the Phase I and II pancreatic tumor vaccine trials. In experiments involving over 400 mice, use of irradiated GM-CSF secreting tumor cells caused only reversible lymphadenopathy and reversible subcutaneous swelling; no ulcerations were seen. In our first phase I trial in patients with renal cell carcinoma, only local erythema and swelling were seen following intradermal injections of cell doses up to 4×10^7 GM-CSF modified vaccine cells, and up to 4×10^8 unmodified vaccine cells.

At the highest dose level, we predict that initially 45 mcg of total GM-CSF will be secreted locally per 24 hours, a level that will diminish as tumor cells are killed by invading inflammatory cells. To support hematologic recovery in oncology patients after intensive chemotherapy, subcutaneous or intravenous doses of GM-CSF between 5 and 10 ug/kg/day are commonly used (350-700 mcg total for a 70 kg individual). At this dose range the following side effects are commonly seen: local or generalized skin rashes, bone pain (attributed to stimulation of hematopoietic progenitors), fever, and malaise. Although patients in the initial Phase I study of the allogeneic tumor vaccine had normal bone marrow function, leukocytosis and toxic levels of serum GM-CSF did not occur with the 10 fold lower dose of GM-CSF. The maximum serum GM-CSF level obtained was 14.0 pg/ml with dose level four at 48 hours after the first pancreatic tumor vaccine.

The plasmid used to transfect the GM-CSF gene is safe. In contrast to retroviral vectors, it lacks the coding sequences that would allow replication and the generation of helper virus. This plasmid containing the GM-CSF gene has been sequenced following vector construction to confirm its insertion, orientation, and the lack of mutations. In addition, this vector has been confirmed to produce bioactive GM-CSF.

The risk of generating autoimmune reactions is unknown but is believed to be small. The pancreas would be the most likely organ to be involved. Pancreatitis and loss of pancreatic function can be supported by the use of exogenous pancreatic enzymes and insulin injections if needed. Other organs that may share tissue specific antigens might also be involved, such as the salivary glands and other gastrointestinal organs. In the Phase I and II studies there were no evidence of autoimmune reactions.

Every patient who has received the vaccine will be evaluated for toxicity. The research participant will be taken off-study if unacceptable adverse events are experienced. Possible toxicities include local swelling, induration, or ulceration at the site of the vaccine, systemic toxicities from paracrine secretion of GM-CSF, and induction of autoimmunity. Patients will be evaluated on days 1 and 3 by a research nurse following the semi-annual or annual vaccination boosting to monitor for local and systemic toxicities. The research participant may be contacted by phone or e-mail or the information may be obtained from their local health care providers. The research participant will be advised to call the research nurse and/or the principal investigator if there are any new toxicities, concerns or questions.

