Data and samples may be obtained from Day-28 to Day 0

1. A clinical evaluation to include vital signs, ECOG status, weight, review of systems, physical examination, and toxicity evaluation.

2. CT scans of the abdomen, pelvis, and chest. If the CT scan is not done at Hopkins, the research participant must provide the report and a copy of the scans. If the research participant is allergic to the CT scan contrast or is contraindicated, a non-contrast CT of the chest and a MRI of the abdomen and pelvis will be obtained.
3. A leukapheresis for in vitro studies will be encouraged. If the research participant refuses a leukapheresis, approximately 200 cc of blood will be drawn. As of Amendment #8, research bloods are no longer required to be collected.
4. Blood testing to include CBC/diff, absolute eosinophils, absolute neutrophils, absolute lymphocytes, comprehensive chemistry panel including electrolytes, albumin, BUN, creatinine, AST, ALT, total bilirubin, and alkaline phosphatase, amylase, and CA 19-9.
5. Research blood: 20 cc for serum banking. As of Amendment #8, research bloods are no longer required to be collected.
6. Pregnancy test for women of childbearing potential. Urine pregnancy test preferred.
7. If not previously enrolled on IRB # NA_00036444 (SKCCC J0248) entitled, Long term follow-up of patients who received lethally irradiated allogeneic pancreatic tumor cells transfected with the GM-CSF gene, the research participant will be encouraged to join the long-term follow-up study.

Day 0

1. Administration of vaccine (Topical lidocaine-based anesthetic may be placed about 1-2 hours prior to planned vaccine administration time to the intended vaccine sites.)
2. Vital signs before and after vaccine administration
3. Photograph of vaccine sites (if clinically indicated)
4. Assessment for toxicities
5. Monitor for 30 minutes after vaccine administration
6. Tetanus toxoid boost if last tetanus vaccination > 10 years. Tetanus/diphtheria (Td) may be substituted if tetanus alone is not available. If both are not available, no tetanus vaccine will be administered.

Day 28 after Boost Vaccine (-3/ + 14 days)

1. A leukapheresis for in vitro studies will be encouraged. If the research participant refuses a leukapheresis, approximately 200 cc of blood will be drawn. As of Amendment #8, research bloods are no longer required to be collected.
2. Assessment for toxicities and vaccine site reactions from previous vaccinations, and medications.

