If the research participant is unable to return to Johns Hopkins for the off-study visit, effort will be made to obtain medical records that may include laboratory and imaging tests results, pathology reports, and health care providers' notes. Data may also be obtained regarding toxicity and disease status by study clinician contact with the research participant, his/her family, or health care providers. The surveys may be mailed to the research participant's home with a stamped return envelope. Fax and electronic correspondence for the diaries and surveys is also acceptable. Arrangements may be made for the research samples to be obtained locally and shipped to the Hopkins' [name] Lab.

If the off-study visit is within 28 days of a protocol-specified visit in which the assessments and samples were obtained, the off-study assessments and specimens need not, but may be, repeated.

Research Samples

De-identified samples may be shared with other investigators with written authorization from the principal investigator. Additional samples may be collected for research purposes, including, but not limited to those obtained through biopsies, surgeries, and autopsies. As of Amendment #8, research bloods are no longer required to be collected.

Table 3. Study schema including toxicity and immune monitoring for Prime Vaccine #1 and each Boost Vaccination.

Assessment	Day 0 ¹	Day 1	Day 2	Day 3	Day 4				Day 28 ²
Clinical evaluation	X								
CT abd/chest/pelvis	X								
Vital signs ³	X	X ⁴		X ⁴					X ¹⁰
Toxicity assessment/evaluation ⁵	X	X ⁴		X ⁴					X ^{5,6}
Vax site assessment ⁵		X ⁴		X ^{4,6}					X ^{5,6}
Heme/ diff/abs.eos	X								
Chemistries ⁷	X								
CA 19-9	X								
Amylase	X								
Leukapheresis or PBL in vitro studies ⁸	X								X
Research blood: HLA typing and EBV testing ⁹	X								
Research blood: Serum banking ⁸	X								
Vaccine site biopsy ⁸	X ⁹								
Photograph, if indicated ⁹	X	X ⁶		X ⁶					X ⁶

¹ May be done up to 28 days prior to Day 0. Additional leukapheresis may be performed for an interesting immunological response.

² Day 28 (-3/ +14 days) assessments and samplings are to be done after each vaccination.

³ Vital signs include temperature, pulse rate, respiration rate, and blood pressure

⁴ At first vaccination only.

⁵ Assess to resolution.

⁶ Information may be obtained by phone, e-mail, fax, and/or through the evaluation by the local health care provider, if unable to assess in person.

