3.4.5 Continuation of Therapy

Provided there is no radiographic evidence of pancreatic cancer disease recurrence, no dose limiting toxicities, and the vaccine is available, the patient will receive an equal mixture of allogeneic pancreatic cancer cell lines Panc 10.05 and Panc 6.03 for a total dose of 5×10^8 vaccine cells divided equally into six intradermal injections to be given as two in each anterior upper thigh and two in the non-dominant upper arm (unless contraindicated) twice every year.

In the event that a research participant has evidence of persistent vaccine-related responses (including, but not limited to: vaccine site flares such as recurrent erythema, induration, and pruritus at previous vaccine administration sites; urticaria) occurring at the frequency of more than once in the previous three months, the research participant may choose to delay the semi-annual or annual boost vaccination for up to one year after the last vaccine-related response. The research participant may also choose to continue to receive the semi-annual or annual boost vaccinations per protocol with evidence of persistent vaccine-related responses. Research participants experiencing urticaria must wait at least one month since the last hive before receiving another vaccine.

The same study schema (Table 3.) that includes toxicity and immune monitoring will be followed with each semi-annual or annual vaccination.

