4.2 Analysis of Primary Endpoint: Safety and toxicity measurements

The primary endpoint of this study is safety as measured by local and systemic toxicity. These toxicities will be characterized according to the National Cancer Institute Common Terminology Criteria for Adverse Events, Version 3.0, and can be accessed and downloaded via the website: <http://ctep.cancer.gov/reporting>. Dermatologic toxicity measurements of the vaccine sites will be performed. For each patient cohort (vaccine naïve and vaccine treated), we will tabulate the number, type and degree of toxicities for each round of vaccination. In addition, we will estimate the proportion of individuals who have a DLT within the first 28 days of vaccination for each round with an exact 95% confidence interval.

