5.2.2 Biopsy of Vaccine Site

Patients will be observed for signs of local inflammation and induration. If responses in this trial are similar to the responses observed in the Phase I and II allogeneic pancreatic tumor vaccine studies, marked inflammatory responses will be present between days 1 and 3. A baseline 3 mm punch biopsy will be obtained for vaccine naïve research participants only. Additional skin biopsies may be obtained, if clinically indicated. Vaccine sites may be photographed before injections and before biopsies. The biopsy sites will be anesthetized with local 1% lidocaine with 1:100,000 epinephrine.

Half of the biopsy specimen will be formalin fixed for hematoxylin and eosin stains. The other half of each biopsy specimen will be snap frozen in OCT for immunohistochemistry stains including; T cell staining (antiCD3), macrophage staining (Ham56), dendritic cell staining (S100), B cell staining (antiCD20), and cytokeratin staining (for presence of tumor cells).

To semiquantitate the immune infiltration, the slides will be interpreted without knowledge of the research participant's information. The type of immune cells infiltrating the vaccine site adjacent to the vaccine cells will be determined using the immunohistochemical stained slides. In addition, a semiquantitative estimate of the proportion of each infiltrating cell type will be determined using a grid to count the number of each cell type per number of tumor cells in that field. These methods for semiquantitation have been successfully employed in the renal vaccine trial. These results will be compared with the biopsy results from our previous vaccine trials.

The biopsy of the vaccine site should not significantly jeopardize any potential therapeutic benefit for the patient. The amount of vaccine and the number of responding immune cells removed by this biopsy is believed to be small.

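### Section 3.4.3 promises day 1 and 3 evaluation after boosts, but Table 3 and the boost visit list omit it after vaccination #1, so by-round toxicity counts may not be comparable

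*Combined protocol and SAP*

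**What the plan says.** Four parts of the combined protocol and SAP set out how toxicity is looked for after a boost.

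- Section 3.4.3: "Patients will be evaluated on days 1 and 3 by a research nurse following the semi-annual or annual vaccination boosting". It adds: "The research participant may be contacted by phone or e-mail or the information may be obtained from their local health care providers".
- Table 3 in section 3.4.1 is titled "Study schema including toxicity and immune monitoring for Prime Vaccine #1 and each Boost Vaccination". Footnote 4, attached to every Day 1 and Day 3 cell for vital signs, toxicity and vaccine-site assessment, reads "At first vaccination only".
- Section 3.4.5: "The same study schema (Table 3.) that includes toxicity and immune monitoring will be followed with each semi-annual or annual vaccination".
- The boost visit list in section 3.4.1.4 has a pre-vaccination window, a Day 0 with 30 minutes of monitoring, and then "Day 28 after Boost Vaccine (-3/ + 14 days". It has no Day 1 or Day 3 entry, and no item for issuing or collecting a diary. The text that follows, on participants who cannot return for the day 28 visit after a boost, nevertheless mentions sending in diaries.

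On the analysis side, section 4.2 makes toxicity the primary endpoint and says, for each cohort, "we will tabulate the number, type and degree of toxicities for each round of vaccination". On timing, section 5.2.2 expects that, if responses resemble those in the earlier trials, "marked inflammatory responses will be present between days 1 and 3".

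**The concern.** The primary objective covers the safety of both primary and boost vaccinations, and the primary analysis is laid out round by round. A reader of that table will naturally look across the rows. If vaccination #1 is examined on the days when local reactions peak and later boosts are asked about only some four to six weeks afterwards, the rows are not measured alike. A fall in the number or grade of reactions from the first vaccination to the boosts could come partly or wholly from the schedule, and could be taken as evidence that boosting is well tolerated. The reactions at issue are common: section 2.8.2 reports transient induration and erythema in all participants of the phase II study.

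**Working it through.** The plan gives no figure for ascertainment by round, so the check is a comparison of the schedules.

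**1. Does footnote 4 apply to boosts?** Yes. The table's title limits it to prime #1 and the boosts, so a restriction to the first vaccination can only exclude later boosts. Section 3.4.5 confirms that the table is the schedule for each boost.

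**2. Does the remote-contact sentence in section 3.4.3 remove the conflict?** No. It changes how the day 1 and 3 evaluation may be done. Footnote 4 removes the evaluation itself. Remote collection has its own footnote (6).

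**3. Scheduled assessments side by side.**

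| Round | Days 1 and 3: toxicity and site assessment | Next toxicity assessment | Diary item |
|---|---|---|---|
| Vaccination #1, both cohorts (3.4.1.1, Table 3) | Listed, with measured erythema and induration | Day 28 | Issued on Day 0 |
| Primes #2 and #3, naive cohort (3.4.1.2, 3.4.1.3) | Not listed | Day 28 | Issued and collected |
| Later boosts, by Table 3 and 3.4.1.4 | Excluded or not listed | Day 28 | Not listed |
| Later boosts, by 3.4.3 | Promised, remote contact allowed | Day 28 | Not addressed |

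**4. Counts.** Assessments after Day 0, through the Day 28 visit:
- vaccination #1: Days 1, 3 and 28 = 3
- later boosts by Table 3 and the list: Day 28 = 1
- later boosts by section 3.4.3: Days 1, 3 and 28 = 3

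The Day 28 window after a boost runs from 28 − 3 = day 25 to 28 + 14 = day 42. That is 25 − 3 = 22 to 42 − 3 = 39 days after the end of the expected peak.

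**5. Which boosts are exposed?** Section 3.4.1.1 makes vaccination #1 a prime for naive patients and the first boost for previously vaccinated patients. The gap therefore covers every boost in the naive cohort (up to 45 patients, section 4.1) and every boost after the first in the previously vaccinated cohort (up to 17).

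**6. Size.** If a Day 28 assessment captures a share *s* of the reactions that day 1 and 3 assessment would record, then tabulated rate = *s* × true rate. The documents give no value for *s*, so only the direction (*s* ≤ 1) can be stated.

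**7. Does it reach the halting rule?** The exact (Clopper-Pearson) 95% interval for 6 of 20 is 11.89% to 54.28%, which reproduces the 11.89% in section 4.1. That rule counts DLTs within 28 days of the first vaccine, where the day 1 and 3 assessments are scheduled, so it is not affected.

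**The case against.** The strongest reply is that section 3.4.3 is an explicit commitment and that vaccination and monitoring take place in one outpatient center. If its staff follow section 3.4.3, most of the asymmetry disappears. Other capture also exists. Section 6.1 records all adverse events from day 0 to 28 of every cycle, Table 3 footnote 5 asks for assessment to resolution, and participants are told to call about new toxicities. The contrast with vaccination #1 is also softer than it looks, because the Day 3 site assessment there may be done remotely (footnote 6). Section 4.2 specifies no test or contrast between rounds, and closer observation at first exposure is a legitimate design.

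Much of this stands, and it limits the point. It does not remove it: the documents do not say which instruction governs, and the table and the visit list agree with each other against section 3.4.3. A general duty to record events does not supply measurements for days on which no assessment is scheduled.

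A reader might infer several stronger things that the documents do not support:
- *Boosts will look safer.* This follows only if Table 3 and the list are followed over section 3.4.3.
- *No boost has day 1 and 3 data.* The first boost of the previously vaccinated cohort does.
- *Boosts have no diary.* The list omits one, but section 3.4.1.4 presupposes diaries at the day 28 visit after a boost, and the appended form has an open field for the vaccine.
- *Primes #2 and #3 breach the plan.* No passage promises day 1 and 3 evaluation after them.

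**Conclusion.** Wrong as written: the documents contradict themselves on how the primary endpoint is collected after boosts. If staff follow Table 3 and section 3.4.1.4, later boosts rest mainly on one assessment between days 25 and 42, and transient local and low-grade reactions may be under-counted relative to vaccination #1. The direction rests on two premises: that reactions peak on days 1 to 3, as section 5.2.2 expects, and that some are missed or graded less exactly weeks later. The size is unknown.

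It would be a mistake to extend this to the main safety decisions. DLTs and serious events are less likely to escape the day 0 to 28 recording duty and the Day 28 assessment, and the interim rule uses the first vaccine only. The point concerns the tabulation of milder reactions and any reading across its rows.

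**What to change.** 1. Reconcile section 3.4.3, Table 3 footnote 4, the section 3.4.1.4 list and the diary instructions, so that one stated boost schedule applies. Which schedule that is remains for the sponsor to decide.
2. In section 4.2, report toxicity by round together with the ascertainment actually used in that round (day 1 and 3 contact or not, in person or remote, diary or not). State that no trend is read across rounds collected differently.
3. Compare rounds only on the Day 28 assessment common to all, using what was elicited at that assessment. Note that after primes #1 and #2 it falls on the next priming visit (28 ± 3, days 25 to 31), against days 25 to 42 after prime #3 and the boosts.

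The cost is small: corrections to one table and the visit lists, and a few sentences in section 4.2. If the day 1 and 3 evaluation is kept, it means two contacts per boost that section 3.4.3 already promises and allows to be remote. The diary form already exists. For rounds already given, items 2 and 3 need only a record of what was done.

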3.4.4 Interval Health Care

The research participant disease status may be evaluated more frequently than twice a year. Patients may undergo additional abdomen, chest and pelvis CT scans and blood tests, including CA 19-9 levels, as recommended by their local oncology, or by the study team as standard of care for possible disease recurrence. The results of the CT scans, blood tests, and progress notes will be requested from the research participant's local oncologist. Medical records obtained will be added to the oncology outpatient medical records, including electronic forms, when possible. Data related to the toxicity and/or disease status assessments will be recorded in the case report form binders and electronic data base.

If the research participant is followed at Johns Hopkins, the medical records will be accessed at least quarterly, and more frequently, if needed for disease recurrence.

If patient is taken off study, the patient's medical records will be requested from the health care provider providing further care for 28 days after the last research product was administered, or longer for resolution of any adverse events related to the research product. After off-study, the research participant will be followed annually via the protocol application number NA_00036444, entitled, "Long-term follow-up of patients who receive lethally irradiated allogeneic pancreatic tumor cells transfected with the GM-CSF gene", SKCCC J0248, if consent is granted.

3.4.5 Continuation of Therapy

Provided there is no radiographic evidence of pancreatic cancer disease recurrence, no dose limiting toxicities, and the vaccine is available, the patient will receive an equal mixture of allogeneic pancreatic cancer cell lines Panc 10.05 and Panc 6.03 for a total dose of 5×10^8 vaccine cells divided equally into six intradermal injections to be given as two in each anterior upper thigh and two in the non-dominant upper arm (unless contraindicated) twice every year.

In the event that a research participant has evidence of persistent vaccine-related responses (including, but not limited to: vaccine site flares such as recurrent erythema, induration, and pruritus at previous vaccine administration sites; urticaria) occurring at the frequency of more than once in the previous three months, the research participant may choose to delay the semi-annual or annual boost vaccination for up to one year after the last vaccine-related response. The research participant may also choose to continue to receive the semi-annual or annual boost vaccinations per protocol with evidence of persistent vaccine-related responses. Research participants experiencing urticaria must wait at least one month since the last hive before receiving another vaccine.

The same study schema (Table 3.) that includes toxicity and immune monitoring will be followed with each semi-annual or annual vaccination.

